## **8.2. Handling of Withdrawals**

The investigator will be requested to collect all patient data until she leave the study treatment. If a subject will be withdrawn by the Investigator or withdraws from the study, the Investigator will complete and report the observations as thoroughly as possible up to the date of withdrawal including the date of last treatment and the reason for withdrawal.

If the subject is withdrawn due to an adverse event, the Investigator will follow the subject until the adverse event has resolved or stabilized.

All patients who are withdrawn from the study should complete protocol specified withdrawal procedures.

## **8.3. Reserve and Replacement Subjects**

Patients who withdraw or are withdrawn from the study prior to completing the first cycle for reasons other than toxicity will be replaced.

# **9. INVESTIGATIONAL PRODUCT**

## **9.1. Investigational product description**

### **9.1.1. Binimetinib**

#### **9.1.1.1. Description**

Binimetinib is supplied as film-coated tablets in a dosage strength of 15 mg.

### **9.1.1.2. Packaging**

Binimetinib 15 mg are packaged in blister packs containing 12 tablets. Each pack contains 168 tablets.

### **9.1.1.3. Shipping, Storage and Disposal**

Binimetinib film-coated tablets should not be stored above 25°C and should be protected from light.

Any unused medicinal product or waste material should be disposed of in accordance with local requirements.

### **9.1.1.4. Dosage and administration**

Patients will receive continuous binimetinib at 45 mg/BID. Binimetinib dose may be reduced to 30 mg/BID according to tolerance and investigator's criteria. Dose re-escalation is allowed in case toxicities are recovered and no new events are present in at least 28 days.

Patients should be encouraged to take their dose at approximately the same time each day. If the patient vomits or misses a dose, an additional dose should not be taken that day. The next prescribed dose should be taken at the usual time.

Binimetinib tablets are intended for oral administration with water; tablets should be swallowed whole and should not be chewed. Binimetinib may be taken without regard to food.

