## 6. STUDY DESIGN

## 6.1. Overall design

This is an interventional, prospective, multicentric, single-arm, open label, phase IB clinical trial.

The following scheme depicts the basic trial design.

Patients diagnosed of metastatic or locally advanced non-curable TNBC that have received at least one treatment regimen for advanced disease will be candidates for the trial. A fresh tumor sample will be obtained in order to determine the phosphoproteomic profile of the tumor preferably obtained after last treatment or the most recent sample as possible (from metastatic site or first diagnosis according to sample availability) prior to study inclusion. If the patient has not a tumor sample available prior to study inclusion, the patient will not be allowed to participate in the study. Activation of the two kinases of interest will be determined centrally at CNIO. Only patients with scores above the upper quartile of at least one of them will be candidates (according to our series, approximately 40% of the patients are positive for CDK4/6 and/or ERK).

Patients will then start treatment with continuous oral binimetinib 45 mg/BID and palbociclib 100 mg daily, 21 days on / 7days off, until disease progression. Tumor evaluation will be performed every 8 weeks. Study treatment will continue until disease progression, unacceptable toxicity, intercurrent serious disease, consent withdrawal or investigator's decision.

If treatment tolerance is good (no side effects or at most tolerable grade 1 side effects) after a full cycle (28 days) patients will be allowed to escalate palbociclib to 125, according to the study investigators' decision. Alternatively, patients with non- tolerable grade 2 events will resume at 30 mg/BID of binimetinib upon recovery, maintaining palbociclib at 100 mg 21-on/7-off. Depending on the side-effects, in case of clear relationship with palbociclib is established, palbociclib -instead of binimetinib – will be reduced to 75 mg daily.

The study will be conducted at 8 Spanish sites and will enroll 25 patients.

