### Palbociclib dose modification and management – Haematological toxicities

CTCAE Grade	Dose modifications
Grade 1 or 2	No dose adjustment is required.
Grade 3 a	
Day 1 of cycle: Withhold palbociclib, until recovery to Grade <math>\leq 2</math>, and repeat complete blood count monitoring within 1 week. When recovered to Grade <math>\leq 2</math>, start the next cycle at the same dose.
 
Day 15 of first 2 cycles: If Grade 3 on Day 15, continue palbociclib at the current dose to complete cycle and repeat complete blood count on Day 22. If Grade 4 on Day 22, see Grade 4 dose modification guidelines below.
 
Consider dose reduction in cases of prolonged (<math>>1</math> week) recovery from Grade 3 neutropenia or recurrent Grade 3 neutropenia on Day 1 of subsequent cycles.

Grade 3 ANC b ( $<1000$ to $500/\text{mm}^3$ ) + Fever $\geq 38.5^\circ\text{C}$ and/or infection	
At any time: Withhold palbociclib until recovery to Grade <math>\leq 2</math> Resume at next lower dose.

Grade 4 a	
At any time: Withhold palbociclib until recovery to Grade <math>\leq 2</math>. Resume at next lower dose.

Grading according to CTCAE 4.0. ANC=absolute neutrophil counts; CTCAE=Common Terminology Criteria for Adverse Events; LLN=lower limit of normal.
 
a Table applies to all haematological adverse reactions except lymphopenia (unless associated with clinical events, e.g., opportunistic infections).
 
b ANC: Grade 1: ANC <math>< \text{LLN} - 1500/\text{mm}^3</math>; Grade 2: ANC <math>1000 - < 1500/\text{mm}^3</math>; Grade 3: ANC <math>500 - < 1000/\text{mm}^3</math>; Grade 4: ANC <math>< 500/\text{mm}^3</math>.
	

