### 9.3.2. Binimetinib

For patients receiving 45 mg binimetinib twice daily, the recommended reduced dose of binimetinib is 30 mg twice daily. Dose reduction below 30 mg twice daily is not recommended. Therapy should be discontinued if the patient is not able to tolerate 30 mg orally twice daily.

If the adverse reaction that resulted in a dose reduction is under effective management, dose re-escalation to 45 mg twice daily may be considered. Dose re- escalation to 45 mg twice daily is not recommended if the dose reduction is due to left ventricular dysfunction or any Grade 4 toxicity.

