### Recommended dose modifications for binimetinib for selected adverse reaction.

Severity of adverse reaction a	Binimetinib
Cutaneous reactions	
• Grade 2	Binimetinib should be maintained. If rash worsens or does not improve within 2 weeks with treatment, binimetinib should be withheld until improved to Grade 0 or 1 and then resumed at the same dose if first occurrence or resumed at a reduced dose if recurrent Grade 2.
• Grade 3	Binimetinib should be withheld until improved to Grade 0 or 1 and resumed at the same dose if first occurrence or resumed at a reduced dose if recurrent Grade 3.
• Grade 4	Binimetinib should be permanently discontinued.
Ocular events	
• Symptomatic retinal pigment epithelial detachments (RPED) (Grade 2 or 3)	Binimetinib should be withheld for up to 2 weeks and ophthalmic monitoring should be repeated including visual acuity assessment. 

• If improved to Grade 0 or 1, binimetinib should be resumed at same dose.

• If improved to Grade 2, binimetinib should be resumed at a lower dose.

• If not improved to Grade 2, binimetinib should be permanently discontinued.

• Symptomatic RPED (Grade 4) associated with reduced visual acuity (Grade 4)	Binimetinib should be permanently discontinued.
• Retinal vein occlusion (RVO)	Binimetinib should be permanently discontinued.

Severity of adverse reaction a	Binimetinib
Cardiac events	

 
Grade 2 Left ventricular ejection fraction (LVEF) decrease or asymptomatic, absolute decrease in LVEF of greater than 10 % from baseline that is below lower limit of normal (LLN)
 
	
LVEF should be evaluated every 2 weeks.
 
 
If asymptomatic: Binimetinib should be withheld for up to 4 weeks. Binimetinib should be resumed at a reduced dose if all of the following are present within 4 weeks: 
 
LVEF is at or above the LLN
 
Absolute decrease from baseline is 10 % or less.
 
 
 
If the LVEF does not recover within 4 weeks, binimetinib should be permanently discontinued.
 

 
Grade 3 or 4 LVEF decrease or symptomatic left ventricular dysfunction (LVD)
 
	
Binimetinib should be permanently discontinued. LVEF should be evaluated every 2 weeks until recovery.

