## **10.2. Study treatment visits**

Study patients will be evaluated weekly during the first 2 months and every 2 weeks thereafter.

The following procedures will be performed during study treatment:

- Tumor evaluation: PET-CT, CT and/or MRI (every 8 weeks)
- Physical examination: will be performed at screening and thereafter targeting symptoms in subsequent study visits
- Ophthalmological examination: Ask patient for changes in vision at every visit. If change in vision is reported, an ophthalmological examination must be performed preferably within 3 days. Ophthalmologic examination will be performed weekly during first cycle, biweekly during second cycle and every 4 weeks thereafter. Particularly for patients who experience any decrease in visual acuity, or symptomatic or asymptomatic retinal disorders including retinal detachment / RPED / serous retinopathy / retinal vein occlusion (Grade 1 analog to CTCAE v.5) have to undergo ophthalmologic examinations on day 1 of every cycle.
- Weight: in all study visits

- Vital Signs: pulse, blood pressure and temperature; every week during first two cycles, and days 1 and 15 of each cycle thereafter
- ECOG performance status (day 1 of every cycle)
- 12-lead ECG: if clinically indicated
- ECHO/MUGA: before start binimetinib treatment, 4 weeks after the start of treatment and every 12 weeks thereafter.
- Hematology: every week during first two cycles, and days 1 and 15 of each cycle thereafter
- Biochemistry: every week during first two cycles, and days 1 and 15 of each cycle thereafter. Safety laboratory tests can be collected up to 2 days prior to drug administration.
- TSH, fT3 y fT4: day 1 of every cycle. Free T3 and free T4 will only be measured if TSH is abnormal.
- Coagulation: day 1 of every cycle
- Urinalysis: day 1 of every cycle
- Serologies: if clinically indicated
- Pregnancy Testing: every 4 weeks (day 1 of each cycle). Pre-menopausal women of childbearing potential only
- Adverse events: in all study visits
- Concomitant medications: in all study visits
- Blood sample: two CPT tubes of 7 ml will be obtained before treatment administration at D1C1 and D1C2.

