### 12.2. Sample size

Patients with advanced TNBC that have received and experienced disease progression to the first/second line treatment are candidates to this trial. Patients that have received three or more treatment lines would be excluded.

Sample size has been calculated based on the primary objective of this clinical trial, to determine 3-months PFS of the palbociclib plus binimetinib in advanced TNBC, in patients with activation of ERK and/or CDK4/6.

Previous studies shown that the 3-months PFS in patients receiving chemotherapy in advanced TNBC was about 25% [44]. To accept the treatment efficacy we will assume that the 3-months PFS in patients treated with palbociclib plus binimetinib will be at least 50%. An overall sample size of 25 patients achieves 80% power at a 0.05 significance level (alpha) to accept the efficacy of palbociclib plus binimetinib in advanced TNBC. An accrual time of 12 months and follow-up time of 12 months (treatment and follow-up time) and 2 sided test have been considered in the sample size calculation.

Sample size has been calculated with one-sample survival method [45].

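### Sections 9.1.1.4 and 9.3.2 of the Protocol set different conditions for returning binimetinib to 45 mg BID, and only 9.3.2 carries the caution after left ventricular dysfunction or Grade 4 toxicity

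*Protocol*

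**What the plan says.** Two places in the Protocol govern the return of binimetinib from 30 to 45 mg BID.

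- **Section 9.1.1.4 (Dosage and administration):** "Dose re-escalation is allowed in case toxicities are recovered and no new events are present in at least 28 days". The sentence is a permission and has no exception by type or grade of toxicity.
- **Section 9.3.2 (Binimetinib, under Criteria for dose adjustments):** the condition is "If the adverse reaction that resulted in a dose reduction is under effective management", in which case re-escalation may be considered. Neither full recovery nor a waiting period is required. The section adds that re-escalation "is not recommended if the dose reduction is due to left ventricular dysfunction or any Grade 4 toxicity".

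Neither section mentions the other. The design text (5.2 and 6.1), the withdrawal criteria (8.1), the treatment-duration text (9.2), the binimetinib dose-modification tables and the SAP contain no other rule on binimetinib re-escalation and no order of precedence.

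**The concern.** The two rules can give different answers for the same patient. A site relying on 9.1.1.4 alone could return a patient to the dose at which an LVEF decrease occurred, which 9.3.2 advises against. A site relying on 9.3.2 alone could re-escalate a reaction that is controlled but not resolved, or one that resolved less than 28 days ago, which 9.1.1.4 does not allow.

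The cardiac case is foreseeable. Section 5.2 lists decreased LVEF among the reasons for reduction to 30 mg BID in an earlier melanoma study, where 61% of patients needed a reduction. Eight sites will apply the text independently. What is at stake is patient safety and uniform dosing, not the primary analysis.

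**Working it through.** **Side-by-side reading**

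| Feature | 9.1.1.4 | 9.3.2 |
|---|---|---|
| State of the reaction | recovered | under effective management |
| Event-free interval | at least 28 days | none |
| Exception | none | left ventricular dysfunction, any Grade 4 toxicity |
| Force | allowed | may be considered / not recommended |
| Reference to the other section | none | none |

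**Which patients can reach the question**

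1. *Asymptomatic LVEF decrease.* The cardiac row of the binimetinib table holds the drug for up to 4 weeks and then states: "Binimetinib should be resumed at a reduced dose if all of the following are present within 4 weeks". These patients are on 30 mg BID with a recovered toxicity, so the two sections diverge for them. Grade 3 or 4 LVEF decrease and symptomatic left ventricular dysfunction lead to permanent discontinuation and do not arise.
2. *Grade 4 events.* A first Grade 4 transaminase elevation, or another first Grade 4 reaction, may be resumed at a reduced dose under the tables in 9.3.2. This route is narrow. Section 8.1 lists Grade 4 non-hematological toxicity as a possible reason for withdrawal. Grade 4 haematological toxicity is handled in 9.3.1 by holding and reducing palbociclib. Section 6.1 reduces palbociclib rather than binimetinib "in case of clear relationship with palbociclib is established". The documents give no rate for this case.
3. *Controlled but unresolved reactions.* These fail 9.1.1.4 and qualify under 9.3.2.

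**How many patients in the cardiac case**

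Inputs:
- 25 patients (section 6.1).
- Left ventricular dysfunction in 6-8% (section 11.3.6), assumed to carry over to this combination.
- Echocardiogram or MUGA "before start binimetinib treatment, 4 weeks after the start of treatment and every 12 weeks thereafter" (section 10.2).
- LVEF re-checked every 2 weeks during a hold of up to 4 weeks (cardiac row, 9.3.2).
- 3-month PFS of 50% (the design assumption: "3-months PFS in patients treated with palbociclib plus binimetinib will be at least 50" per cent) or 25% (chemotherapy reference), both from section 12.2.

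Further assumptions: the decrease is found at the week-4 scan; the 28 days run from resumption; PFS is exponential and unrelated to the cardiac event; 3 months = 13 weeks.

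- Patients with any event: 0.06 × 25 = 1.5; 0.08 × 25 = 2.0.
- Earliest re-escalation: 4 + (2 to 4) + 4 = week 10 to 12, that is 6 to 8 weeks after detection.
- Proportion still progression-free, S^(t/13):
  - at 50%: 0.5^(6/13) = 0.726 and 0.5^(8/13) = 0.653;
  - at 25%: 0.25^(6/13) = 0.527 and 0.25^(8/13) = 0.426.
- Expected patients:
  - at 50%: 1.5 × 0.653 = 0.98 to 2.0 × 0.726 = 1.45;
  - at 25%: 1.5 × 0.426 = 0.64 to 2.0 × 0.527 = 1.05.

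These counts come before removal of Grade 3/4, symptomatic and unrecovered cases, and of patients with a new event within the 28 days.

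**Size of the dose step:** 2 × 30 = 60 mg/day to 2 × 45 = 90 mg/day; 90/60 = 1.5, an increase of 50%.

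**The case against.** The strongest reply is that nothing here is contradictory. All sections of a protocol apply together, and 9.1.1.4 can be read as a general permission that 9.3.2 limits for named toxicities. A site that reduces the dose for an LVEF decrease must also use the table in 9.3.2, and the caution stands just above that table. So the site would have to use the section and overlook its opening text. This makes a misreading less likely. It does not remove the difference, because 9.1.1.4 is a natural place to look up a dosing rule and does not point onward.

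The numbers are also an upper bound, and that stands. The 28-day condition, read literally, excludes patients with any new event, and the estimate makes no deduction for this. The estimate also places every event at the week-4 scan. The next scheduled scan is about week 16, when on the same model only 0.5^(16/13) = 43% or 0.25^(16/13) = 18% would be progression-free. Re-escalation would then fall at about weeks 22 to 24 (16 + 2 to 4 + 4), close to the end of the planned 6-month treatment participation.

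Finally, the caution is advisory, so repeating it does not forbid re-escalation. Requiring recovery also removes an option that 9.3.2 alone would give, for example for hypertension controlled on treatment. Both are true. However, 9.1.1.4 already requires recovery, so a site following both sections has no such option now.

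**Conclusion.** The concern holds. The Protocol states two different conditions for the same dosing step, does not say that both apply, and gives the caution after left ventricular dysfunction or Grade 4 toxicity in only one of them. This is an unreconciled difference rather than a strict contradiction, but it can lead to different actions for the same patient.

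The size is small. About one patient in 25, and probably fewer, would reach the cardiac case. That figure depends on the 6-8% rate carrying over, detection at week 4, and exponential PFS unrelated to the cardiac event. The Grade 4 case is rarer and cannot be quantified from the documents. The sample size, the primary endpoint and its analysis are untouched. The wording should be corrected because the possible harm is cardiac, the right caution is already in the Protocol, and the correction is cheap.

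**What to change.** Put one joint rule in 9.3.2 and replace the re-escalation sentence in 9.1.1.4 with a cross-reference to it. Suggested content: re-escalation to 45 mg BID may be considered only once toxicities have recovered and at least 28 days have passed without a new event; it "is not recommended if the dose reduction is due to left ventricular dysfunction or any Grade 4 toxicity". This keeps the conditions of 9.1.1.4 and the caution of 9.3.2 in its own words, so it adds no new clinical criterion.

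The cost is one sentence and a cross-reference in a protocol amendment, with no extra visits, patients or analyses. The downside is that a few patients will stay at 30 mg BID longer or permanently, including some whose reaction is controlled but not resolved. If the sponsor wants to keep re-escalation open for that last group, the rule should say so explicitly.

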## **9.1.2. Palbociclib**

### **9.1.2.1. Description**

Palbociclib are opaque, hard capsules with 75, 100 and 125 mg of palbociclib.

### **9.1.2.2. Packaging**

Palbociclib 75 mg, 100 mg and 125 mg are packaged in blister packs of 21 hard capsules. PVC/PCTFE/PVC/Al blister strip containing 7 hard capsules (one capsule per cell). Each carton contains 21 hard capsules (3 blister strips per pack).

### **9.1.2.3. Shipping, Storage and Disposal**

Palbociclib does not require any special storage conditions.

Any unused medicinal product or waste material should be disposed of in accordance with local requirements.

#### **9.1.2.4. Dosage and administration**

Patients will receive palbociclib on day 1 at 100 mg per day until day 21 followed by a 7-day rest. Palbociclib may be escalated to 125 mg per day according to tolerance and investigator's criteria, starting in cycle 2.

Patients should be encouraged to take their dose at approximately the same time each day. If the patient vomits or misses a dose, an additional dose should not be taken that day. The next prescribed dose should be taken at the usual time.

Palbociclib should be taken with food, preferably a meal and should not be opened. Capsules are intended for oral administration with a glass of water; capsules should be swallowed whole and should not be chewed or crushed.

#### **9.2. Treatment duration**

Treatment will continue until disease progression, unacceptable toxicity, significant intercurrent disease, consent withdrawal or investigator's decision.

In case of discontinuation/interruption for toxicity of one of the 2 drugs of the combination therapy during treatment, the continuation of patient in the study with the other drug will be agreed with study sponsor (depending on the duration of treatment, if she has benefit, if the benefit is attributed to the suspended drug, etc.).

#### **9.3. Criteria for dose adjustments**

##### **9.3.1. Palbociclib**

Dose modification of palbociclib is recommended based on individual safety and tolerability. Management of some adverse reactions may require temporary dose interruptions/delays, and/or dose reductions, or permanent discontinuation as per dose reduction schedules provided in Tables 1, 2, and 3.

#### **Palbociclib recommended dose modifications for adverse reactions**

Dose level	Dose
Recommended dose	125 mg/day
First dose reduction	100 mg/day
Second dose reduction	75 mg/day*

\*If further dose reduction below 75 mg/day is required, discontinue the treatment.

Complete blood count should be monitored prior to the start of palbociclib therapy and at the beginning of each cycle, as well as on Day 15 of the first 2 cycles, and as clinically indicated.

For patients who experience a maximum of Grade 1 or 2 neutropenia in the first 6 cycles, complete blood counts for subsequent cycles should be monitored every 3 months, prior to the beginning of a cycle and as clinically indicated.

Absolute neutrophil counts (ANC) of  $\geq 1.000/\text{mm}^3$  and platelet counts of  $\geq 50.000/\text{mm}^3$  are recommended to receive palbociclib.

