Recent preclinical studies suggest that alternating schedules (continuous palbociclib administration plus 3 weeks on/1 off MEK inhibitor, or continuous MEK inhibitor plus 3 weeks on/1 off palbociclib) are more effective and better tolerated in animals than continuous dosing of both agents alone [41]. We propose to use as starting dose that one found as RP2D in a similar study ongoing in lung cancer that has already completed the safety lead-in part (NCT03170206, data on file). In this study binimatinib 45 mg BID was the recommended phase II dose [42]. Another study with binimatinib and palbociclib in colorectal cancer (NCT03981614) uses the same starting doses of both drugs without a preceding dose-escalation phase. A subsequent study in a larger number of patients in advanced melanoma showed that a significant number (61%) of patients had to undergo dose reduction to 30 mg/BID because of the former side effects and others such as hypertension, decreased LVEF or elevated CPK [43]. Some of these toxicities partially overlap with those already registered for palbociclib, such as diarrhea and decreased blood counts. So we propose to start on 45 mg/BID (binimatinib, continuous dosage) plus 100 mg daily (palbociclib, days 1-21/28). If tolerance is good (no side effects or at most tolerable grade 1 side effects) after a full cycle (28 days) patients will be allowed to escalate palbociclib to 125, according to the study investigators' decision. Alternatively, patients with non-tolerable grade 2 events will resume at 30 mg/BID of binimatinib upon recovery, maintaining palbociclib at 100 mg 21-on/7-off. Depending on the side-effects, in case of clear relationship with palbociclib is established, palbociclib - instead of binimatinib – will be reduced to 75 mg daily.

We propose a single-arm pilot trial testing palbociclib + binimatinib (CDK4/6 plus MEK inhibition) in advanced TNBC to evaluate preliminary activity of this combination by measuring 3-months PFS.

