**Table 3. Palbociclib dose modification and management – Non-haematological toxicities**

CTCAE Grade	Dose modifications
-------------	--------------------

Grade 1 or 2	No dose adjustment is required.
Grade $\geq 3$ non-haematological toxicity (if persisting despite medical treatment)	Withhold until symptoms resolve to: - Grade $\leq 1$ ; - Grade $\leq 2$ (if not considered a safety risk for the patient)  Resume at the next lower dose.
Grading according to CTCAE 4.0. CTCAE=Common Terminology Criteria for Adverse Events.	

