### **3.10. Study treatment**

Patients will then start treatment with continuous oral binimetinib 45 mg/BID and palbociclib 100 mg daily, 21 days on / 7days off, until disease progression. Study treatment will continue until disease progression, unacceptable toxicity, intercurrent serious disease, consent withdrawal or investigator’s decision.

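### Protocol 9.3.1 conflicts with the trial's own palbociclib text on palbociclib-related, non-tolerable Grade 2 events, and its dose-level labels do not match the 100 mg start

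*Protocol*

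**What the plan says.** **Starting dose and escalation.** Protocol 9.1.2.4 states: "Patients will receive palbociclib on day 1 at 100 mg per day until day 21 followed by a 7-day rest". Protocol 5.2 and 6.1 give the same start, and SAP 3.10 repeats it: "palbociclib 100 mg daily, 21 days on / 7days off, until disease progression". The higher dose is optional: "Palbociclib may be escalated to 125 mg per day according to tolerance", from cycle 2 and at the investigator's discretion.

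**Dose-level table in Protocol 9.3.1.** It has three rows: 125 mg/day as the recommended dose, 100 mg/day as the "First dose reduction", and 75 mg/day as the second. Its footnote sets the floor: "If further dose reduction below 75 mg/day is required, discontinue the treatment".

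**Grade 2 events in Protocol 5.2 and 6.1.** The default acts on the other drug: "patients with non-tolerable grade 2 events will resume at 30 mg/BID of" binimetinib once recovered, with palbociclib kept at 100 mg. The exception is an event with a clear relationship to palbociclib. In that case palbociclib, rather than binimetinib, "will be reduced to 75 mg daily".

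**Grade 2 events in Protocol 9.3.1.** The haematological and non-haematological palbociclib tables each have one row for Grade 1 or 2, and in both it reads "No dose adjustment is required". Neither has an exception for non-tolerable events. The introduction to 9.3.1 presents these tables as the schedules for interrupting, reducing or stopping palbociclib.

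**The concern.** A site managing palbociclib toxicity will turn to the tables in 9.3.1. For one kind of event they lead to a different action from the one set out in 5.2 and 6.1. The dose-level table also describes a ladder that begins above the dose at which every patient in this trial begins. With 8 sites and 25 patients, a few events handled differently would be visible in the exposure and tolerability results. Before that, it is a safety matter: two operative instructions in one protocol disagree, and following the protocol as written does not settle which applies.

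**Working it through.** No sample-size or power figure is involved. The check sets the passages side by side and counts the dose steps.

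**1. Grade 2 instruction**

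| Event | Protocol 5.2 and 6.1, palbociclib | Protocol 9.3.1 tables, palbociclib | Agree? |
|---|---|---|---|
| Grade 2, tolerable | no reduction ordered | no adjustment required | yes |
| Grade 2, non-tolerable, no clear link to palbociclib | kept at 100 mg (binimetinib is reduced) | no adjustment required | yes |
| Grade 2, non-tolerable, clear link to palbociclib | reduced to 75 mg daily | no adjustment required | **no** |

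This takes the sentence on palbociclib in 5.2 and 6.1 as the alternative to the sentence just before it, so that it carries the same non-tolerable Grade 2 condition. The conflict is then confined to the third row. The binimetinib table for other adverse reactions in 9.3.2 does have an entry for recurrent or intolerable Grade 2 reactions. The palbociclib tables have no counterpart, so the gap lies on the palbociclib side.

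**2. Dose-level labels**

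Inputs: levels of 125, 100 and 75 mg/day (9.3.1), a start of 100 mg/day (5.2, 6.1, 9.1.2.4, SAP 3.10), and a floor of 75 mg/day (9.3.1 footnote).

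- Steps down the printed ladder: 125 → 100 → 75, which is 2 reductions.
- Steps down from the actual start: 100 → 75, which is 1 reduction.
- Change for an unescalated patient if the row labelled as the first reduction is read literally: 100 − 100 = 0 mg.
- Steps down for a patient escalated to 125 mg: 2, which matches the ladder.

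The mismatch therefore concerns patients who have not been escalated.

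**3. Does the label change the dose given?**

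Where the toxicity tables order a reduction, they say to resume at the next lower dose and do not refer to a numbered reduction. From 100 mg the next lower level is 75 mg. That equals the figure in 5.2 and 6.1, and the floor agrees with the withdrawal criterion in 8.1. A site that follows the action wording reaches 75 mg whatever the row is called.

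**The case against.** The strongest defence is that the ladder works in practice. 125 mg is a permitted dose in this trial, so the three rows cover every palbociclib level a patient can receive, and the next-lower-dose wording gives a consistent step from each. On Grade 2, the introduction to 9.3.1 frames the changes as recommendations based on individual tolerability. An adjustment that is not required is also not forbidden, so 6.1 could be read as the specific rule and the tables as the general one.

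The first part stands and limits the labelling problem to wording. The second is a possible reading but not one the protocol states. One text says the dose will be reduced and the other says no adjustment is needed, and no rule of precedence is given.

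A reader might also infer more than the documents support:

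- **That all 25 patients face conflicting instructions.** All start at 100 mg, but the Grade 2 conflict arises only with a particular event, and the ladder fits any patient escalated to 125 mg.
- **That the dose-level table contains a Grade 2 dose rule.** It does not. The Grade 2 rows are in the two toxicity tables.
- **That the SAP's exposure results depend on this ladder.** A denominator of 125 mg would give a fully compliant 100 mg patient a relative dose intensity of (21 × 100)/(21 × 125) = 2100/2625 = 80%, instead of 100%. But SAP 7.2 counts reductions without citing the table, SAP 7.3 uses the dose due per protocol, and SAP 3.10 gives that dose as 100 mg. Nothing directs the analyst to 125 mg.

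**Conclusion.** The point holds in two parts of unequal weight.

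The Grade 2 conflict is a real contradiction between operative safety instructions. It is limited to non-tolerable Grade 2 events with a clear relationship to palbociclib. The documents give no expected frequency for such events, so the number of patients affected cannot be estimated from them.

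The dose-level labels are a mismatch of wording: one reduction step from the actual start against two on the printed ladder, for unescalated patients only. No different dose has been shown to follow, because the next lower dose from 100 mg is 75 mg under either text.

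The conclusion assumes that the clear-relationship sentence in 5.2 and 6.1 applies to the non-tolerable Grade 2 events of the preceding sentence, and that no text outside these two documents sets precedence. It takes no position on which dose or rule is right.

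**What to change.** The sponsor should reconcile the dose-level table and the two palbociclib toxicity tables in Protocol 9.3.1 with Protocol 5.2, 6.1 and 9.1.2.4 and with SAP 3.10. After that, the dose-level labels should agree with the dosing text, and the instruction for non-tolerable Grade 2 events related to palbociclib should be the same wherever it appears. The content of the reconciled rule is for the sponsor and clinical investigators to decide.

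The cost is wording. Protocol 14.3 requires an amendment for any protocol change, but sample size, endpoints and analysis methods are unaffected. SAP 3.10 would need editing only if the reconciled dosing text differs from what it now says.
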